For this pilot, we propose to consent up to 24 Veterans age 60-95 years with chronic musculoskeletal pain with the goal of having 18 Veterans initiate vEAET treatment (i.e., planning for at least 25% dropout, consistent with our prior studies). Modest funds will be used from the PI's Career Development Award to provide a tablet for each Veteran. Each Veteran will receive one 90-minute individual session of vEAET plus eight 90-minute weekly group sessions of vEAET, all delivered over VTC to Veterans' homes. The study will plan to include 3 vEAET groups, each with 6 Veterans. We will use VA Video Connect (VVC) as the primary VTC platform, with Zoom Version 5.0 (Zoom Video Communication, San Jose, CA) as the back-up platform. Assessments will include satisfaction ratings, pain ratings, and psychosocial functioning, and will be performed at baseline, posttreatment, and 2-month follow-up. We will perform all assessments remotely using OutcomeMD (Los Angeles, CA), a HIPAA-compliant and VA-approved web-based platform. The goal is to perform the entire study remotely without any in-person visits. The Specific Aims are:

1. Acceptability and Feasibility. In 18 Veterans age 60-95 years with chronic musculoskeletal pain, assess recruitment, treatment adherence, treatment credibility, and patient satisfaction to vEAET.
2. Limited-Efficacy Testing and Estimated Effect Size. Assess the effects of vEAET on pain severity, pain interference, psychosocial functioning, depression, anxiety, and social connectedness from baseline to posttreatment and 2-month follow-up and calculate estimated effect sizes for a subsequent RCT.
3. Select Measures for Mediation/Moderation of Treatment Response. Veterans will complete validated measures on pain attitudes, cognitive/behavioral coping, and technological literacy to determine the feasibility of using these measures for future assessment of mediation/moderation in a subsequent RCT.

2. Background/Significance

Chronic pain is one of the most common and costly conditions treated at VA. Rates of chronic pain peak during late middle-age and older adulthood, reaching rates as high as 80% in older Veterans (1, 2). Given the recent "opioid crisis," DoD and VA have prioritized non-pharmacologic treatments as first line for chronic pain, and evaluation of non-pharmacologic treatments for chronic pain is a VA ORD priority area (3).

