Sample, Recruitment. We will recruit up to 24 Veterans age 60-95 years from two of the PI's open studies ([name] 2017-070668 and 2019-020112), which are both clinical trials of in-person psychotherapy for chronic pain, through our clinical sites, and using the VISN 22 Data Warehouse. For patients recruited from the open studies, we will only recruit patients who gave their permission to be contacted about future studies on the consent form. Only participants in these studies who did not previously undergo in-person EAET will be eligible (i.e., we will only recruit patients who completed CBT but not EAET or were randomly assigned to EAET but who dropped out prior to receiving any EAET sessions). Eligible participants will receive a letter/flyer via U.S. mail. If there is no contact established after 2 weeks, no more than 2 telephone calls will be made to invite them to participate in the current study. If there is no response after 2 calls, attempts to contact will cease. Second, Veterans will be recruited from outpatient sites at the West Los Angeles VA Medical Center (WLA), including Geriatric Psychiatry, Neuropsychiatry, GRECC, Neurobehavior, Chronic Pain, Interventional Pain, Women's, PCMHI, and Primary Care Clinics. Before clinic, a medical chart review is performed to determine whether potential participants meet basic inclusion/exclusion criteria. Clinicians will ask identified patients whether they consent to be contacted by the research team and will document if patients reply in the affirmative with a note in CPRS and copy a member of the research team as an additional signer. Third, we will

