VTC Equipment, Participant Payments. Consistent with other studies of VTC psychotherapy for older adults (9, 10), we will furnish all participants with equipment to complete all VTC sessions and self-report assessments in

their homes. Following receipt of completed consent/HIPAA forms, the RC will send each participant a tablet computer via secure U.S. mail purchased using funds from the PI's VA Career Development Award (CDA). The RC will then provide telephone consultation with participants to instruct them on how to open and complete the self-report assessments and join VTC sessions. The RC will record the amount of time needed to train each participant, which will be reported as a feasibility outcome. Participants will be allowed to keep these tablets following their participation as compensation for their time and inconvenience of completing the training and baseline assessments (value: approximately \$100). In addition, participants will be compensated \$25 for their time upon completion of the posttreatment and 2-month follow-up questionnaires (\$50 total for each participant).

Sites. All research activities take place at the West Los Angeles VA Medical Center (WLA). Veterans participate remotely from their homes

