Fidelity Monitoring. All vEAET therapy sessions will be video recorded for the purposes of fidelity monitoring. In this pilot, an RC will complete a standardized checklist (attached) on a randomly-selected 25% of sessions to ensure that the sessions covered targeted topics. This is performed for the purposes of quality assurance. Participants will consent to the production of video recording at the time of informed consent by completing HIPAA authorization. Videos are encrypted, labeled with an alphanumeric code, and produced using VA-approved software directly onto our encrypted VA research server protected by 128-bit SSL, the secure socket layer technology used for sensitive transactions on the web (pathway R:\RES_Geripsych_Research). The system is accessible only via the VA intranet and employs a hierarchical system of password protected logins, allowing differential access to project team members as appropriate to their roles. The PI and his team have extensive experience conducting studies that have required creating data systems such as this for encrypted electronic files.

Analysis Plan. Prior to performing the primary analyses, descriptive statistics and graphical summaries are obtained for all baseline measures to check for missing data, outliers, and the need for transformations or non-parametric methods, and to obtain characteristics of the sample. We will perform descriptive statistics (e.g., means, standard deviations, frequencies) to evaluate acceptability (satisfaction, credibility) and feasibility variables (attendance, time spent training on VTC equipment). To evaluate within-treatment effects on outcomes, we will use paired-samples t-tests comparing baseline to posttreatment and baseline to follow-up scores on all efficacy outcomes. Within-treatment effect sizes will be calculated using the formula: $d = (\text{post [or follow-up] } M - \text{baseline } M) / \text{SD of change scores}$. To determine the frequency of individual cases having improvement in pain, we use the standard metric of 30% improvement, as well as the moderately stringent criterion of 50% improvement, and the very stringent criterion of 70% improvement. If some missing values are present due to attrition, we use a conservative estimation approach by assuming no change from the previous assessment and replacing missing follow-up data with the last available point (i.e., last observation carried forward).

4. Safety

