We plan to complete this pilot over a 12-month period. We anticipate consenting 24 and enrolling 18 Veterans. The IRB application will be submitted in June 2020. The first group is anticipated to begin in September 2020. The groups should be completed by the end of February 2021. We have allowed 3 months at the end of the study to carry out data cleaning and analysis and to begin abstract, manuscript, and grant writing. Please see

the timeline in **Table 2**. Unless participants give permission to bank their data for future research, it will be destroyed 6 years from the end of the fiscal year after completion of the research project.

Task Month	Jun	Jul	Aug	Sep	Oct	Nov	Dec	Jan	Feb	Mar	Apr	May
IRB application & approval	X	X										
Contact potential participants		X	X	X	X							
Enrollment/baseline assessments (n=12)			X	X	X	X						
vEAET				X	X	X	X	X	X			
Posttreatment assessments					X	X	X	X	X			
2-month follow-up assessments							X	X	X	X		
Interim and final data analyses							X	X	X	X		
Abstract and manuscript preparation										X	X	X
Prepare and submit Merit Review										X	X	X

7. References

3. Group TOTfCPW. VA/DoD Clinical Practice Guideline for Opioid Therapy for Chronic Pain. Washington, DC: VA/DoD; 2017 February 2017.
6. [name] BC, Lumley MA, Cassidy JT, Steers WN, Osato S, Schubiner H, et al. Emotional Awareness and Expression Therapy (EAET) Achieves Greater Pain Reduction than Cognitive Behavioral Therapy (CBT) in Older Adults with Chronic Musculoskeletal Pain: A Preliminary Randomized Comparison Trial. *Pain Med*. 2020;e-published ahead of Print.

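### Does recruitment, named in Aim 1, need its own planned analysis when the Analysis Plan omits it and Table 2 prints n=12?

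*Combined protocol and SAP*

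**What the plan says.** Section 1 lists four things for Aim 1 to cover: the study will "assess recruitment, treatment adherence, treatment credibility, and patient satisfaction to vEAET". It allows up to 24 consents "with the goal of having 18 Veterans initiate vEAET treatment", with a planned dropout of 25% or more and three groups of six.

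Section 3 (Sample, Recruitment) gives the same ceiling: "We will recruit up to 24 Veterans age 60-95 years". It describes three sources: two existing trials, clinic referrals and a data warehouse search. For Veterans approached by mail from the trials, as for the warehouse group, telephone follow-up is limited: "If there is no response after 2 calls, attempts to contact will cease".

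Section 3 (VTC Equipment, Participant Payments) says of training time: "The RC will record the amount of time needed to train each participant, which will be reported as a feasibility outcome". No matching sentence exists for recruitment. The Analysis Plan then promises descriptive statistics for satisfaction and credibility and for "feasibility variables (attendance, time spent training on VTC equipment".

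Section 6 states: "We anticipate consenting 24 and enrolling 18 Veterans". Table 2, directly below that text, labels one row "Enrollment/baseline assessments (n=12" and marks it from August to November.

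**The concern.** Three of the four Aim 1 items reach the Analysis Plan: adherence (as attendance), credibility and satisfaction. Recruitment does not, and the list of feasibility variables is not worded as a set of examples. No denominator is named, whether Veterans mailed, reached, screened or eligible, and no number is declared as the standard for judging recruitment. The one figure printed against the enrollment months disagrees with the rest of the protocol.

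In a pilot meant to prepare an RCT, the worry is freedom after the fact. The team could choose which milestone counts as recruited, over which base and against which goal, and the same result could then be presented as on target or as half of target.

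**Working it through.** **Inputs.** 18 treatment starts, up to 24 consents, 25% dropout and 3 groups of 6 (Section 1); 24 consented and 18 enrolled (Section 6 text); n=12 over four marked months (Table 2).

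**1. The plan's own figures.** Consents needed = starts / (1 - dropout) = 18 / (1 - 0.25) = 24. Group places = 3 x 6 = 18. Both stated numbers reproduce.

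**2. Can 12 be another milestone?**
- As treatment starts, it would need 12 / 0.75 = 16 consents. No 16 appears.
- As consents, it would leave 12 x 0.75 = 9 starts. No 9 appears.
- As group places, 12 / 6 = 2 groups, not three.
- As baselines alone, it fails too. Every Veteran who starts treatment needs a baseline for the paired comparisons, so 18 starts require at least 18 baselines.

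Twelve therefore cannot be reconciled with the text. It looks like a leftover from a two-group plan, though the documents do not say so.

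**3. What the label could distort.** If 12 were enrolled: 12/12 = 100%, 12/18 = 67%, 12/24 = 50%. Pace over four months: 12/4 = 3, 18/4 = 4.5, 24/4 = 6 per month. These compare different milestones (baseline, start, consent), and the first depends on treating a row label as a target. Section 1 states the goals of 24 and 18, Section 3 repeats each of them, and the Section 6 text repeats both. The 12 appears once. No formula, test or stopping decision refers to it.

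**4. What a prespecified recruitment analysis would add.** The output would be counts and simple proportions.
- Consent to start: if the plan were met exactly, 18/24 = 75%, exact (Clopper-Pearson) 95% interval 53% to 90%. This is a planning ratio, used here only to show the precision available.
- By source: assuming an equal split, 24/3 = 8 consents each. An illustrative 6 of 8 has an exact interval of 35% to 97%.
- Contact yield: the documents give no number contacted. With assumed bases of 60, 120 or 240, 24 consents would be 40% (28% to 53%), 20% (13% to 28%) or 10% (7% to 15%). Consents are capped at 24, so once the cap is reached the yield is set by how many Veterans were approached. That number is known only afterwards.

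Prespecification would fix a form of words. It would not change the quantities or make them more precise.

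**The case for a change.** The strongest case for a change is that recruitment is the first item in Aim 1 and the only one dropped, while the protocol shows with training time that it can specify a feasibility outcome. Aim 1 is also framed in the 18 treated Veterans, and recruitment cannot be measured within people already recruited. Some Veterans come from the investigator's own trials, so a pooled yield may not carry over to the RCT. Section 3 (Consent, Screening) has prior identifying screening information destroyed, so counts not kept along the way might be lost. One sentence would settle all of this cheaply.

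The omission stands, and so does the contradiction in Table 2. The consequences are weaker than they look:
- The destruction rule concerns identifying information, in a sequence about Veterans who have signed consent; it does not require discarding counts. Clinic referrals are documented in the medical record, and the mailings are made to identified patients.
- Reasons for refusal cannot be collected from Veterans who never respond, because calls stop after two attempts. A fuller breakdown would therefore be incomplete however it was specified.
- Section 5 says the pilot data will address inexperience with the platforms, help select measures and supply effect sizes for power. It does not promise an accrual projection. A pilot capped at 24 consents would be a poor basis for one, and the RCT's size is not given.
- The size of the prior-trial pool is not stated, so whether a pooled yield would mislead cannot be judged from the documents.

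**Conclusion.** No change to the plan follows. The missing recruitment line is a gap in detail that analysts fill sensibly: the goals of 24 consented and 18 starting are on record, the first product listed in Section 5 is a manuscript on acceptability and feasibility, and the natural report is a participant flow set against those goals. The n=12 in Table 2 is a clerical slip in a timeline label. It differs from the text by 6 (18 - 12) or 12 (24 - 12), and no analysis uses it.

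The size of the issue is one of four Aim 1 items without a stated descriptive summary and one unreconciled label. Nothing changes in any hypothesis test, effect estimate, error rate or sample size. The conclusion assumes that the coordinator keeps ordinary counts of Veterans approached and screened, and that the write-up judges recruitment against 24 and 18. It would need revisiting only if the study intended a formal go/no-go rule based on recruitment, and the documents contain none.

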Potential Benefits. The study will be of direct relevance and benefit to older Veterans who suffer from chronic pain. All study participants will receive a psychological intervention, vEAET, which may be helpful for pain and related symptoms, such as depression and anxiety. Results from the study will inform future research on psychological interventions for chronic pain over VTC, which we anticipate will ultimately be helpful to improve access to this treatment for Veterans who are impacted by COVID-19 related social distancing or who cannot or prefer not to come into VA for care.

Risk/Benefit Ratio. The risks of this study are small. We will be gaining valuable information to help improve our understanding of the potential use of vEAET for older Veterans with chronic pain and help inform future research aimed at using alternate psychological treatment strategies for older Veterans with chronic pain.

Alternatives to Participation. The patient may receive ongoing medical care in their respective clinics, including in primary care, pain clinic, etc. for pain whether or not s/he participates in the study. This includes medications and interventional pain approaches (e.g. injections, ketamine). The VA also offers a chronic pain rehabilitation program, cognitive behavior therapy for chronic pain, and physical and occupational therapy for chronic pain. Mindfulness classes, acupuncture, and other complementary/integrated medicine approaches are also offered. The patient may elect to not participate, and this will not adversely affect any ongoing care at the VA.

5. List of Anticipated Research Products

1. Scientific abstract and manuscript reporting on the acceptability, feasibility, and initial efficacy testing of vEAET for older Veterans with chronic musculoskeletal pain.
2. The main "product" will be a strong VA Merit Review application that will include an RCT comparing vEAET with an alternative in this population. These pilot data will be used to address potential limitations related to the lack of prior experience with the VTC and online assessment platforms. These data will also help select measures and estimate effect sizes for subsequent power analyses for the RCT. If the Merit is funded, study start-up can be accelerated due to our experience with the materials and methods.

6. Project Timeline

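### The planned effect size has no small-sample correction, so with 18 Veterans d overstates the true standardised change by about 4.7% on average

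*Combined protocol and SAP*

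**What the plan says.** The Analysis Plan in section 3 gives one effect-size definition for all efficacy outcomes. "Within-treatment effect sizes will be calculated using the formula" whose numerator is the posttreatment or follow-up mean minus the baseline mean, and whose denominator is the "SD of change scores". Neither a small-sample correction nor the divisor of the SD is mentioned.

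Estimating effect sizes for a later RCT is part of Aim 2 in section 1. Section 5 repeats the purpose: "These data will also help select measures and estimate effect sizes for subsequent power analyses for the RCT".

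Three other statements determine which n applies:

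- **Sample size.** Section 1 plans to consent up to 24 "with the goal of having 18 Veterans initiate vEAET treatment (i.e., planning for at least 25% dropout, consistent with our prior studies"). Section 6 agrees: "We anticipate consenting 24 and enrolling 18 Veterans". The stated dropout therefore falls between consent and the start of treatment.
- **Attrition.** For missing values the Analysis Plan says "we use a conservative estimation approach by assuming no change from the previous assessment" and describes "replacing missing follow-up data with the last available point (i.e., last observation carried forward").
- **Timeline.** Table 2 in section 6 has a row labelled "Enrollment/baseline assessments (n=12"), which does not agree with 18 or 24.

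**The concern.** A sample mean divided by a sample SD is a biased estimator of the corresponding population ratio. The SD in the denominator varies from sample to sample, and the average of one over a sample SD exceeds one over the true SD. In expectation, d is therefore pushed away from zero, and the fewer the degrees of freedom, the larger the push. With 17 degrees of freedom the effect is visible in the second decimal.

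In many pilots this would not be worth a comment. Here, effect-size estimation is a declared deliverable, and the values are intended for the power analyses of another trial. The expected bias has the same sign relative to zero for every efficacy outcome at both time points, so averaging over outcomes does not remove it. What is at stake is a modest optimism in the estimator on which a grant application will draw, and a known factor removes it.

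**Working it through.** **Inputs.** From the documents: the definition of d (Analysis Plan), 18 Veterans starting treatment (sections 1, 3 and 6), and last observation carried forward (Analysis Plan). Assumed, because the documents do not give them: normally distributed change scores, an SD with divisor n - 1, and true standardised changes of 0.3 to 1.0.

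**1. The plan's own figure.** The only sample-size figure is 24 consented to yield 18 treated. 24 × (1 - 0.25) = 18, and 18/0.75 = 24, so it reproduces exactly. The 18 already allows for the stated 25% dropout. No value of d, bias or power is stated, so there is nothing further to reproduce.

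**2. Exact bias factor.** With df = n - 1,

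J(df) = Γ(df/2) / [√(df/2) × Γ((df - 1)/2)], and the mean of d equals the true value divided by J.

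At n = 18, df = 17 and J = 0.9551. Then 1/J = 1.047, an average overstatement of 4.7%. A true 0.80 averages 0.80/0.9551 = 0.838, and a true 0.50 averages 0.50/0.9551 = 0.523.

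**3. Usual approximation.** 1 - 3/(4 × 17 - 1) = 1 - 3/67 = 0.9552, which agrees with the exact factor to within 0.0001.

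**4. Simulation at n = 18, nobody carried forward** (200,000 normal samples per row):

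| True value | Mean d | Mean d / true | SD of d | Share of samples with d above true |
|---|---|---|---|---|
| 0.3 | 0.315 | 1.051 | 0.257 | 51% |
| 0.5 | 0.524 | 1.048 | 0.269 | 51% |
| 0.8 | 0.838 | 1.048 | 0.294 | 52% |
| 1.0 | 1.046 | 1.046 | 0.316 | 52% |

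The average bias is confirmed. It is 0.02 to 0.04 at true values of 0.5 and 0.8, against a sampling SD of 0.27 to 0.29. If the software used divisor n for the SD, mean d / true would be about 1.08 instead.

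**5. Effect of dropout under the planned rule.** Carrying a value forward keeps the Veteran in the comparison, so n stays 18, df stays 17 and J does not change. What changes is the quantity being estimated. If the dropouts are carried forward from baseline as zero change and are otherwise like the rest, mean d / true effect in those treated becomes:

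| Carried forward, of 18 | Mean d / true, over true values 0.3 to 1.0 |
|---|---|
| 2 | 0.92 to 0.98 |
| 4 | 0.81 to 0.91 |
| 5 | 0.76 to 0.87 |

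**6. Whether the correction still has a role then.** Compare d with its own target, the population value when that proportion is carried forward. With up to 4 of 18 carried forward, d stays about 2% to 5% above that target, whereas d × J is within about 2.5% of it.

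**The case against.** The strongest objection is that carrying values forward already pulls d towards zero, so the correction could make matters worse. For the effect in those treated, this has force. At true values of 0.5 and 0.8, one Veteran carried forward from baseline brings mean d / true to 0.99 to 1.01, and multiplying by J takes it to 0.95 to 0.96. With four, 0.85 to 0.89 becomes 0.81 to 0.85. But that offset depends on how many drop out and when, neither of which is known in advance. With no dropout after treatment starts, the full 4.7% remains. Two unrelated biases should not be left to cancel by chance.

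It is also fair to say that the formula is explicit and commonly used, that the pilot's first aim is acceptability and feasibility, and that any reader given d and n can apply J afterwards. A within-group change from an uncontrolled study is in any case not the between-group effect that an RCT needs, and no confidence interval for d is planned. Those limits matter more for planning. They keep this point minor but do not remove it.

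A reader might infer three stronger things, which the documents do not support:

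- **That each reported d is about 5% too large.** The 4.7% is an average. A single d exceeds the true value in only 51% to 52% of samples. At a true 0.80, 95% of values fall between 0.33 and 1.49.
- **That the bias grows with attrition.** The factor for n = 14 (6.3%) belongs to a completers-only analysis, which is not planned. The factor for n = 12 (7.5%) would apply only if the label in Table 2 were the real sample. That label is an inconsistency to reconcile, not an attrition estimate.
- **That the RCT would be planned about 9% too small at n = 18, or 14% at n = 12.** Those figures come from 1 - J², which puts the mean of d into 1/d². A planned N comes from one realised d, and 1/d² is not linear. At n = 18 the median planned N is only about 3% low for true values of 0.5 or more. The mean planned N is too large, by about 24% to 38% when restricted to d above 0.2.

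**Conclusion.** The point holds as a minor one. The Analysis Plan fixes an uncorrected d, the plan sends it to RCT planning, and at n = 18 its expected value is about 4.7% too large in absolute terms. The bias is small beside sampling error and does not increase with dropout under the planned imputation. No systematic shortfall of a stated size in the later trial's N follows from it.

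The 4.7% rests on normal change scores, an SD with divisor n - 1, and 18 Veterans in the comparison. The carried-forward results also assume that dropouts are carried forward from baseline and are otherwise similar to completers. The true values of 0.3 to 1.0 are illustrative.

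**What to change.** Add one line to the Analysis Plan: each within-treatment d is multiplied by 1 - 3/(4(n-1) - 1) and reported as Hedges g for paired change, where n is the number analysed in that comparison, and that n is stated beside the estimate. At n = 18 the multiplier is 0.955. State as well that the SD of change uses divisor n - 1.

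This needs no new data and no design change. The price is a slightly less favourable figure: an observed d of 0.80 would be reported as 0.80 × 0.955 = 0.76. The correction does not address the bias from carrying values forward, so the number of values carried forward in each comparison should be shown next to g. The 12 in Table 2 should be reconciled with the 18 and 24 elsewhere, so that the n behind the multiplier is not in doubt.
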